### Endocrine disorders

Thyroid disorders, adrenal insufficiency, diabetes mellitus, and pituitary disorders have been associated with the administration of atezolizumab. Management guidelines for endocrine events are provided in the table below.

Patients experiencing one or more unexplained AEs possibly indicative of endocrine dysfunction (including headache, fatigue, myalgias, impotence, mental status changes, and constipation) should be investigated for the presence of thyroid, pituitary, or adrenal endocrinopathies. The patient should be referred to an endocrinologist if an endocrinopathy is suspected. Thyroid stimulating hormone (TSH) and free T3 and T4 levels should be measured to determine whether thyroid abnormalities are present. Pituitary hormone levels and function tests [*e.g.*, TSH, growth hormone, luteinizing

hormone, follicle-stimulating hormone, testosterone, prolactin, adrenocorticotrophic hormone (ACTH) levels, and ACTH stimulation test] and MRI of the brain (with detailed pituitary sections) may help to differentiate primary pituitary insufficiency from primary adrenal insufficiency. The table below describes dose management guidelines for hyperthyroidism, hypothyroidism, symptomatic adrenal insufficiency, and hyperglycemia.

Event	Management
Asymptomatic hypothyroidism	
 
Continue atezolizumab.
 
Initiate treatment with thyroid replacement hormone.
 
Monitor TSH weekly.
 

Symptomatic hypothyroidism	
 
Withhold atezolizumab.
 
Initiate treatment with thyroid replacement hormone.
 
Monitor TSH weekly.
 
Consider patient referral to endocrinologist.
 
Resume atezolizumab when symptoms are controlled and thyroid function is improving.
 

Asymptomatic hyperthyroidism	
TSH <math>\geq 0.1</math> mU/L and <math>< 0.5</math> mU/L:
 
 
Continue atezolizumab.
 
Monitor TSH every 4 weeks.
 
 
TSH <math>< 0.1</math> mU/L:
 
 
Follow guidelines for symptomatic hyperthyroidism.
 

Symptomatic hyperthyroidism	
 
Withhold atezolizumab.
 
Initiate treatment with anti-thyroid drug such as methimazole or carbimazole as needed.
 
Consider patient referral to endocrinologist.
 
Resume atezolizumab when symptoms are controlled and thyroid function is improving.
 
Permanently discontinue atezolizumab.
 

Symptomatic adrenal insufficiency, Grade 2–4	
 
Withhold atezolizumab for up to 12 weeks after event onset.a
 
Refer patient to endocrinologist.
 
Perform appropriate imaging.
 
Initiate treatment with corticosteroids equivalent to 1–2 mg/kg/day IV methylprednisolone and convert to 1–2 mg/kg/day oral prednisone or equivalent upon improvement.
 
If event resolves to Grade 1 or better and patient is stable on replacement therapy, resume atezolizumab.b
 
If event does not resolve to Grade 1 or better or patient is not stable on replacement therapy while withholding atezolizumab, permanently discontinue atezolizumab.
 

Hyperglycemia, Grade 1 or 2	
 
Continue atezolizumab.
 

Event	Management
	
 
Investigate for diabetes. If patient has Type 1 diabetes, treat as a Grade 3 event. If patient does not have Type 1 diabetes, treat as per institutional guidelines.
 
Monitor for glucose control.
 

Hyperglycemia, Grade 3 or 4	
 
Withhold atezolizumab.
 
Initiate treatment with insulin.
 
Monitor for glucose control.
 
Consider referral to endocrinologist, particularly if patient is deemed to have atezolizumab-induced diabetes; if so, obtain C-peptide level paired with glucose, autoantibody levels (e.g. GAD65, islet cell autoantibodies), and hemoglobin A1C level.
 
If patient is found to have diabetic ketoacidosis or hyperglycemic hyperosmolar syndrome, treat as per institutional guidelines with appropriate management and laboratory values (e.g. anion gap, ketones, blood pH, etc.) reported.
 
Resume atezolizumab when symptoms resolve and glucose levels are stable.
 

Hypophysitis (pan-hypopituitarism), Grade 2 or 3	
 
Withhold atezolizumab for up to 12 weeks after event onset.a
 
Refer patient to endocrinologist.
 
Perform brain MRI (pituitary protocol).
 
Initiate treatment with corticosteroids equivalent to 1–2 mg/kg/day IV methylprednisolone and convert to 1–2 mg/kg/day oral prednisone or equivalent upon improvement.
 
Initiate hormone replacement if clinically indicated.
 
If event resolves to Grade 1 or better, resume atezolizumab.b
 
If event does not resolve to Grade 1 or better while withholding atezolizumab, permanently discontinue atezolizumab.
 
For recurrent hypophysitis, treat as a Grade 4 event.
 

Hypophysitis (pan-hypopituitarism), Grade 4	
 
Permanently discontinue atezolizumab.
 
Refer patient to endocrinologist.
 
Perform brain MRI (pituitary protocol).
 
Initiate treatment with corticosteroids equivalent to 1–2 mg/kg/day IV methylprednisolone and convert to 1–2 mg/kg/day oral prednisone or equivalent upon improvement.
 
Initiate hormone replacement if clinically indicated.
 

MRI = magnetic resonance imaging; TSH = thyroid-stimulating hormone.

a Atezolizumab may be withheld for a longer period of time (*i.e.*, >12 weeks after event onset) to allow for corticosteroids (if initiated) to be reduced to the equivalent of ≤10 mg/day oral prednisone. The acceptable length of the extended period of time must be determined by the investigator.

b If corticosteroids have been initiated, they must be tapered over ≥1 month to the equivalent of ≤10 mg/day oral prednisone before atezolizumab can be resumed.

#### Ocular events

An ophthalmologist should evaluate visual complaints (e.g., uveitis, retinal events).

Management guidelines for ocular events are provided in the table below.

Event	Management
Ocular event, Grade 1	
 
Continue atezolizumab.
 
Patient referral to ophthalmologist is strongly recommended.
 
Initiate treatment with topical corticosteroid eye drops and topical immunosuppressive therapy.
 
If symptoms persist, treat as a Grade 2 event.
 

Ocular event, Grade 2	
 
Withhold atezolizumab for up to 12 weeks after event onset.a
 
Patient referral to ophthalmologist is strongly recommended.
 
Initiate treatment with topical corticosteroid eye drops and topical immunosuppressive therapy.
 
If event resolves to Grade 1 or better, resume atezolizumab.b
 
If event does not resolve to Grade 1 or better while withholding atezolizumab, permanently discontinue atezolizumab.
 

Ocular event, Grade 3 or 4	
 
Permanently discontinue atezolizumab.
 
Refer patient to ophthalmologist.
 
Initiate treatment with corticosteroids equivalent to 1–2 mg/kg/day oral prednisone.
 
If event resolves to Grade 1 or better, taper corticosteroids over ≥1 month.
 

a Atezolizumab may be withheld for a longer period of time (*i.e.*, >12 weeks after event onset) to allow for corticosteroids (if initiated) to be reduced to the equivalent of ≤10 mg/day oral prednisone. The acceptable length of the extended period of time must be determined by the investigator.

b If corticosteroids have been initiated, they must be tapered over ≥1 month to the equivalent of ≤10 mg/day oral prednisone before atezolizumab can be resumed.

### Immune-mediated Cardiac Events

Immune-mediated myocarditis and pericarditis have been associated with the administration of atezolizumab. Management guidelines for cardiac events are provided in the table below.

### Immune-mediated Myocarditis

Immune-mediated myocarditis has been associated with the administration of atezolizumab. Immune-mediated myocarditis should be suspected in any patient presenting with signs or symptoms suggestive of myocarditis, including, but not limited to, laboratory (*e.g.*, B-NP [B-Natriuretic Peptide]) or cardiac imaging abnormalities, dyspnea, chest pain, palpitations, fatigue, decreased exercise tolerance, or syncope. Myocarditis may also be a clinical manifestation of myositis or associated with pericarditis (see section on pericardial disorders below) and should be managed accordingly.

Immune-mediated myocarditis needs to be distinguished from myocarditis resulting from infection (commonly viral, *e.g.*, in a patient who reports a recent history of gastrointestinal illness), ischemic events, underlying arrhythmias, exacerbation of preexisting cardiac conditions, or progression of malignancy. All patients with possible

myocarditis should be urgently evaluated by performing cardiac enzyme assessment, an electrocardiogram (ECG), a chest X-ray, an echocardiogram, and a cardiac MRI as appropriate per institutional guidelines. A cardiologist should be consulted. An endomyocardial biopsy may be considered to enable a definitive diagnosis and appropriate treatment, if clinically indicated.

Patients with signs and symptoms of myocarditis, in the absence of an identified alternate etiology, should be treated according to the guidelines in the table below.

Event	Management
Immune-related myocarditis, Grade 2	
 
• Withhold atezolizumab for up to 12 weeks after event onseta.
 
• Refer patient to cardiologist.
 
• Initiate treatment as per institutional guidelines and consider antiarrhythmic drugs, temporary pacemaker, ECMO, or VAD as appropriate.
 
• Consider treatment with corticosteroids equivalent to 1–2 mg/kg/day IV methylprednisolone and convert to 1–2 mg/kg/day oral prednisone or equivalent upon improvement.
 
• If symptoms resolve to below Grade 2 (i.e. patient is completely asymptomatic), resume atezolizumab.b
 
• If symptoms do not resolve to below Grade 2 while withholding atezolizumab, permanently discontinue atezolizumab.
 

Immune-related myocarditis, Grade 3-4	
 
• Permanently discontinue atezolizumab.
 
• Refer patient to cardiologist.
 
• Initiate treatment as per institutional guidelines and consider antiarrhythmic drugs, temporary pacemaker, ECMO, or VAD as appropriate.
 
• Initiate treatment with corticosteroids equivalent to 1–2 mg/kg/day IV methylprednisolone and convert to 1–2 mg/kg/day oral prednisone or equivalent upon improvement.
 
• If event does not improve within 48 hours after initiating corticosteroids, consider adding an immunosuppressive agent.
 
• If symptoms resolve to below Grade 2, taper corticosteroids over <math>\geq 1</math> month.
 

ECMO = extracorporeal membrane oxygenation; VAD = ventricular assist device.

a Atezolizumab may be withheld for a longer period of time (*i.e.*, >12 weeks after event onset) to allow for corticosteroids (if initiated) to be reduced to the equivalent of  $\leq 10$  mg/day oral prednisone. The acceptable length of the extended period of time must be documented by the investigator.

b If corticosteroids have been initiated, they must be tapered over  $\geq 1$  month to the equivalent of  $\leq 10$  mg/day oral prednisone before atezolizumab can be resumed.

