**General AE Management and Dose Modification Guidelines**

There will be no dose reduction for atezolizumab in this study.

Patients may temporarily suspend study treatment for up to 84 days (12 weeks) beyond the scheduled date of delayed infusion if study drug-related toxicity requiring dose suspension is experienced. If atezolizumab is held because of AEs for 84 days beyond the scheduled date of infusion, the patient will be discontinued from atezolizumab and will be followed for safety and efficacy as specified in this protocol. If the AE resolves within 84 days and the patient is receiving corticosteroid therapy for the event, atezolizumab may be held for longer than 84 days (up to 4 weeks) in order to allow tapering of the steroid dose to  $\leq 10$  mg oral prednisone or equivalent.

Dose interruptions for reasons other than toxicity, such as surgical procedures, may be allowed. The acceptable length of interruption will be at the discretion of the study PI in consultation with CTEP.

The primary approach to grade 1 to 2 irAEs is supportive and symptomatic care with continued treatment with atezolizumab; for higher-grade irAEs, atezolizumab should be withheld and oral and/or parenteral steroids administered. Recurrent grade 2 irAEs may also mandate withholding atezolizumab or the use of steroids. Assessment of the benefit risk balance should be made by the investigator, with consideration of the totality of information as it pertains to the nature of the toxicity and the degree of clinical benefit a given patient may be experiencing prior to further administration of atezolizumab. Atezolizumab should be permanently discontinued in patients with life threatening irAEs.

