#### Management of Specific AEs

Management of certain AEs of concern, including immune-related pneumonitis, hepatitis, colitis, endocrinopathies, pancreatitis, neuropathies, meningoencephalitis, and potential ocular toxicities are presented in the Atezolizumab Investigator's Brochure. See the Agent Administration Guidelines including the “**Administration of First and Subsequent Atezolizumab Infusions**” table for guidelines for the management of Infusion Related Reactions and Anaphylaxis.

Atezolizumab has been associated with risks such as the following: IRRs and immune-related hepatitis, pneumonitis, colitis, pancreatitis, diabetes mellitus, hypothyroidism, hyperthyroidism, adrenal insufficiency, hypophysitis, Guillain-Barré syndrome, myasthenic syndrome or myasthenia gravis, facial paresis, myelitis, meningoencephalitis, myocarditis, pericardial disorders, nephritis, myositis, and severe cutaneous adverse reactions. Immune-mediated reactions may involve any organ system and may lead to hemophagocytic lymphohistiocytosis and macrophage activation syndrome. Neutropenia and lymphopenia associated with chemotherapy may increase the risk for developing an infection in patients receiving atezolizumab in combination with chemotherapy.

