### Immune-mediated Pericardial Disorders

Immune-mediated pericarditis should be suspected in any patient presenting with chest pain and may be associated with immune-mediated myocarditis (see section on myocarditis above).

Immune-mediated pericardial effusion and cardiac tamponade should be suspected in any patient presenting with chest pain associated with dyspnea or hemodynamic instability.

Patients should be evaluated for other causes of pericardial disorders such as infection (commonly viral), cancer related (metastatic disease or chest radiotherapy), cardiac injury related (post myocardial infarction or iatrogenic), and autoimmune disorders, and should be managed accordingly.

All patients with suspected pericardial disorders should be urgently evaluated by performing an ECG, chest X-ray, transthoracic echocardiogram, and cardiac MRI as appropriate per institutional guidelines. A cardiologist should be consulted. Pericardiocentesis should be considered for diagnostic or therapeutic purposes, if clinically indicated.

Patients with signs and symptoms of pericarditis, pericardial effusion, or cardiac tamponade, in the absence of an identified alternate etiology, should be treated according to the guidelines in the table below. Withhold treatment with atezolizumab for Grade 1 pericarditis and conduct a detailed cardiac evaluation to determine the etiology and manage accordingly.

Event	Management
Immune-mediated myocarditis, Grade 2–4	
 
• Permanently discontinue atezolizumab.
 
• Refer patient to cardiologist.
 
• Initiate treatment as per institutional guidelines and consider antiarrhythmic drugs, temporary pacemaker, ECMO, VAD, or pericardiocentesis as appropriate.
 
• Initiate treatment with corticosteroids equivalent to 1–2 mg/kg/day IV methylprednisolone and convert to 1–2 mg/kg/day oral prednisone or equivalent upon improvement.
 
• If event does not improve within 48 hours after initiating corticosteroids, consider adding an immunosuppressive agent.
 
• If event resolves to Grade 1 or better, taper corticosteroids over <math>\geq 1</math> month.
 

Immune-mediated pericardial disorders, Grade 2–4	

ECMO = extracorporeal membrane oxygenation; VAD = ventricular assist device.

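### Section 8.2.2 gives conflicting instructions on stopping atezolizumab in symptomatic hyperthyroidism and, through an unqualified row label, in Grade 2 myocarditis

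*Combined protocol and SAP*

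**What the plan says.** Section 8.2.2 allows no dose reduction of atezolizumab, so a site can only continue, withhold, resume or stop. The general guidance reserves mandatory stopping for the worst events: "Atezolizumab should be permanently discontinued in patients with life threatening irAEs". Event-specific tables follow.

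- **Endocrine disorders, symptomatic hyperthyroidism.** The row says to withhold, treat as needed and consider referral. It then says "Resume atezolizumab when symptoms are controlled and thyroid function is improving". The next and last bullet, with nothing to qualify it, is "Permanently discontinue atezolizumab" (the same words as in the pericardial table).
- **Endocrine disorders, asymptomatic hyperthyroidism.** For TSH below 0.1 mU/L the instruction is "Follow guidelines for symptomatic hyperthyroidism".
- **Immune-mediated Myocarditis, Grade 2.** The row says to withhold for up to 12 weeks, refer to a cardiologist and consider steroids. Once symptoms are below Grade 2, it reads "patient is completely asymptomatic), resume atezolizumab". If they are not, "If symptoms do not resolve to below Grade 2 while withholding atezolizumab, permanently discontinue atezolizumab". A footnote requires any steroids to be tapered over at least a month, to the equivalent of 10 mg prednisone daily or less, before restarting.
- **Immune-mediated Pericardial Disorders.** The table has a row labelled "Immune-mediated myocarditis, Grade 2–4". Its first action is "Permanently discontinue atezolizumab", and it offers no route back to treatment.

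Management of Specific AEs also points to the Investigator's Brochure. Its list includes "hepatitis, colitis, endocrinopathies, pancreatitis, neuropathies, meningoencephalitis, and potential ocular toxicities are presented in the Atezolizumab" Investigator's Brochure.

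**The concern.** A site cannot both resume a drug and stop it permanently. In the hyperthyroidism row, two sites with identical patients could act in opposite ways and each cite the protocol. The same can happen in Grade 2 myocarditis if one site works from the myocarditis table and another takes the label in the pericardial table at face value.

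Safety is the first matter at stake. In Section 9.4, both myocarditis and hyperthyroidism carry the footnote warning that immune-mediated events of this drug class can be severe and possibly fatal. The second is conduct. Section 13.6 requires on-site verification of treatment administration for all patients at selected sites, yet the text does not tell a monitor which action is correct. The German appendix (Section 1.3, item 5) makes meeting the Section 8.2 stopping criteria a ground for permanent discontinuation, so it inherits the ambiguity.

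The third is the safety description. The adverse event profile of each arm is a secondary objective (Section 2.2), and Section 13.4.3 records events separately for the first 12 cycles and the atezolizumab continuation. A recurrence after restarting can appear only if the site restarted.

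**Working it through.** **Step 1: compare the instructions.** The plan gives no figure to reproduce here.

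- *Hyperthyroidism.* Both instructions are in one row for one population. The resume bullet has a condition (symptoms controlled, thyroid function improving). The stop bullet has none. As printed, a patient who meets the resume condition is also told to stop, and the TSH rule brings asymptomatic patients into the same conflict.
- *Grade 2 myocarditis.* The tables have separate introductions. The myocarditis table is introduced for patients with signs of myocarditis. The pericardial table is introduced for patients with pericarditis, effusion or tamponade. The myocarditis text also refers pericarditis-associated cases to the pericardial section. So the tables can be reconciled, but only by reading a limit into a label that states grades and nothing else.
- *Precedence.* The general rule covers life-threatening events, so it does not decide Grade 2 myocarditis. The Brochure list names endocrinopathies but not myocarditis, and it sets no order of precedence for either.

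**Step 2: treatment at stake for one patient.** Section 7.1 plans 25 atezolizumab doses, or 24 after a pre-registration cycle. Take 25 doses at 14-day intervals, with Grade 2 myocarditis after dose *k*.

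- Permanent stop: 0 further doses.
- Resume, with every held dose made up: 25 − *k*.
- Resume after a full 12-week hold (84 / 14 = 6 cycles), with 12 months as a calendar limit: 25 − *k* − 6.

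For *k* = 6 the last two give 19 and 13. For *k* = 12 they give 13 and 7. The protocol does not say whether held doses are made up.

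**Step 3: number of patients.** Section 9.4 gives frequency bands from 3,097 atezolizumab patients. Applied to the planned 350 adults in Arm 1:

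- Myocarditis is in the under-3% column: 0.03 × 350 = 10.5, so fewer than 11 at any grade.
- No Grade 2 rate is given. At assumed rates *p* of 0.1%, 0.3% and 1%, the expected number 350*p* is 0.35, 1.05 and 3.5. The chance of at least one case, 1 − (1 − *p*)^350, is 0.295, 0.651 and 0.970.
- Hyperthyroidism is in the column up to 20%, without the asterisk that marks rates below 3%: 0.03 × 350 = 10.5 to 0.20 × 350 = 70 at any severity.
- If 10% to 50% of these are symptomatic or have TSH below 0.1 mU/L (an assumption), the row applies to between 0.10 × 10.5 ≈ 1 and 0.50 × 70 = 35 patients.

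**The case against.** The strongest reply concerns myocarditis. Read with their introductions and the cross-reference, the tables serve different populations, and the pericardial table adds pericardiocentesis to its actions. Resumption is also guarded: the patient must be free of symptoms, a cardiologist is involved, and any steroids must first be tapered. Most of this stands, and it is why the myocarditis point is an ambiguous label. It does not remove the point. The same table also lists pericardial disorders of Grade 2–4, so a myocarditis row confined to overlap cases would add little, and a reader may reasonably take it to mean all myocarditis.

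For hyperthyroidism, the general rule suggests that the last bullet was meant for life-threatening disease. A qualifier lost when the PDF was read cannot be excluded. The Brochure, which is not available here, may also give a clear rule. These points indicate the likely intent, but the row as printed still contradicts itself.

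A reader might infer three stronger points that the documents do not support:

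- *That permanent discontinuation is the safer rule for all Grade 2 myocarditis.* This is a clinical preference. The documents do not establish it.
- *That surgical holds are a third contradiction.* Section 8.1.7 removes a patient from protocol therapy after a hold of more than 42 days, while Section 8.2.2 leaves the length of atezolizumab interruptions to the study PI in consultation with CTEP. This can be read as a general limit with a discretion specific to atezolizumab.
- *That the primary result is affected.* Efficacy is analysed by intention to treat (Section 13.0), and patients who stop early remain in follow-up (Section 12.1).

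**Conclusion.** The point holds as a drafting defect in a safety rule. The hyperthyroidism row is self-contradictory as printed. The Grade 2 myocarditis conflict rests on one unqualified label, which its context probably limits to pericardial involvement.

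The consequence is possible inconsistent treatment, and possible re-exposure against intent, in a small number of patients. The patient counts rest on applying the Section 9.4 bands to Arm 1. The Grade 2 myocarditis rates and the symptomatic share of hyperthyroidism are assumptions, and their ranges are too wide to serve as forecasts. The effect on the adverse event comparison is small, because Section 13.4.3 compares overall rates and a patient with the index event is already counted. No sample size, event count, power, alpha or stopping boundary changes.

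The value of a wording change depends on whether anyone is still being dosed, which the documents do not say. The German appendix plans last treatment for February 2023, and the expedited-reporting text in Section 9.3.1 is effective August 2024, so treatment may be over.

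**What to change.** If any patient is still receiving atezolizumab:

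1. In the symptomatic hyperthyroidism row, limit the last bullet to life-threatening hyperthyroidism, in line with the general rule in Section 8.2.2.
2. Relabel the myocarditis row of the pericardial table as myocarditis with pericardial involvement, Grade 2–4. If permanent discontinuation is intended for every Grade 2 myocarditis, rewrite the Grade 2 row of the myocarditis table to say so. Do not simply delete that row, since isolated Grade 2 myocarditis would then have no instruction under its own heading.

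If dosing has ended, add to the safety analysis a listing of the affected Arm 1 cases: Grade 2 or higher myocarditis, and hyperthyroidism that was symptomatic or had TSH below 0.1 mU/L. Show for each whether atezolizumab was resumed, the number of later doses and any recurrence. Code neither stopping nor resuming under the conflicting rows as a protocol deviation.

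The cost is a few words of protocol text, or one listing from adverse event and dosing data already collected. No new visits or tests are needed.

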**8.2.2 Dose Modifications for Atezolizumab**

Administration of atezolizumab will be performed in a setting with emergency medical facilities and staff who are trained to monitor for and respond to medical emergencies.

Premedication is not permitted for the first dose of atezolizumab. Premedication with antihistamines or antipyretics/analgesics (e.g., acetaminophen) may be administered for subsequent infusions at the discretion of the treating physician. The management of Infusion Related Reactions will be according to severity as follows:

- In the event that a patient experiences a Grade 1 Infusion Related Reaction during Cycle 1, the infusion rate should be reduced to half the rate being given at the time of event onset. Once the event has resolved, the investigator should wait for 30 minutes while delivering the infusion at the reduced rate. If tolerated, the infusion rate may then be increased to the original rate.
- In the event that a patient experiences a Grade 2 Infusion Related Reaction, or flushing, fever, or throat pain, the infusion should be immediately interrupted and the patient should receive aggressive symptomatic treatment. The infusion should be restarted only after the symptoms have adequately resolved to baseline grade. The infusion rate at restart should be half of the infusion rate that was in progress at the time of the onset of the Infusion Related Reaction. For subsequent infusions, administer oral premedication with antihistamine and anti-pyretic and monitor closely for Infusion Related Reactions.
- For Grade 3 or 4 Infusion Related Reactions, the infusion should be stopped immediately, and aggressive resuscitation and supportive measures should be initiated (e.g., oral or IV antihistamine, anti-pyretic, glucocorticoids, epinephrine, bronchodilators, oxygen). Atezolizumab should be permanently discontinued. Resumption of atezolizumab may be considered in patients who are deriving benefit and have fully recovered from the immune-related event; retreatment requires consultation with, and consent of, the trial Principal Investigator (PI).

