#### Management Guidelines for Infusion-Related Reactions and Cytokine-Release Syndrome

Event	Management
Grade 1 a Fever b with or without constitutional symptoms	
 
• Immediately interrupt infusion.
 
• Upon symptom resolution, wait 30 minutes and then restart infusion at half the rate being given at the time of event onset.
 
• If the infusion is tolerated at the reduced rate for 30 minutes, the infusion rate may be increased to the original rate.
 
• If symptoms recur, discontinue infusion of this dose.
 
• Administer symptomatic treatment,c including maintenance of IV fluids for hydration.
 
• In case of rapid decline or prolonged CRS (> 2 days) or in patients with significant symptoms and/or comorbidities, consider managing as per Grade 2.
 
• For subsequent infusions, consider administration of oral premedication with antihistamines, anti-pyretics, and/or analgesics, and monitor closely for IRRs and/or CRS.
 

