### Immune-Mediated Myositis

Immune-mediated myositis has been associated with the administration of atezolizumab. Myositis or inflammatory myopathies are a group of disorders sharing the common feature of inflammatory muscle injury; dermatomyositis and polymyositis are among the most common disorders. Initial diagnosis is based on clinical (muscle weakness, muscle pain, skin rash in dermatomyositis), biochemical (serum creatine kinase increase), and imaging (electromyography/MRI) features, and is confirmed with a muscle biopsy.

Patients with signs and symptoms of myositis, in the absence of an identified alternate etiology, should be treated according to the guidelines in table below.

Event	Management
Immune-mediated myelitis, Grade 1	
 
Continue atezolizumab unless symptoms worsen or do not improve.
 
Investigate etiology and refer patient to a neurologist.
 

Immune-mediated myelitis, Grade 2	
 
Permanently discontinue atezolizumab.
 
Investigate etiology and refer patient to a neurologist.
 
Rule out infection.
 
Initiate treatment with corticosteroids equivalent to 1-2 mg/kg/day oral prednisone.
 

Immune-mediated myelitis, Grade 3 or 4	
 
Permanently discontinue atezolizumab.
 
Refer patient to a neurologist.
 
Initiate treatment as per institutional guidelines.
 

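### Section 8.2.2 gives two incompatible atezolizumab rules for Grade 2 immune-mediated myocarditis, and nearby text on myositis and on interruption for surgery also needs reconciling

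*Combined protocol and SAP*

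**What the plan says.** Protocol Section 8.2.2 sets event-specific rules for atezolizumab in a series of tables. Five places matter here.

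- **Myocarditis.** In the Immune-mediated Myocarditis table, the Grade 2 row starts with "Withhold atezolizumab for up to 12 weeks after event onset" (a footnote allows longer for steroid tapering). It lets dosing resume once symptoms are below Grade 2, which it explains as having no symptoms at all, and ends "If symptoms do not resolve to below Grade 2 while withholding atezolizumab, permanently discontinue atezolizumab". Steroids are to be considered. A separate row requires permanent discontinuation at Grades 3-4. The table under Immune-mediated Pericardial Disorders then has a row labelled "Immune-mediated myocarditis, Grade 2–4", next to one for pericardial disorders of the same grades. It opens with permanent discontinuation and tells the site to start steroids.
- **Myositis and myelitis.** The Immune-Mediated Myositis section directs "Patients with signs and symptoms of myositis, in the absence of an identified alternate etiology" to the table beneath it, where every row is labelled myelitis. The Neurologic disorders section announces myelitis guidance in its own table, which contains none.
- **Surgery.** Section 8.1.7 allows study drug to be held for at most 42 days and removes the patient from protocol therapy beyond that. The general adverse-event text of Section 8.2.2 names surgery as a reason for interruption and leaves its length to the study PI in consultation with CTEP.
- **Symptomatic hyperthyroidism.** One cell contains "Resume atezolizumab when symptoms are controlled and thyroid function is improving" and, as its next bullet, permanent discontinuation.
- **Infusion reactions.** For a Grade 1 reaction in Cycle 1, the opening of Section 8.2.2 says "the infusion rate should be reduced to half the rate being given at the time of event onset". The Grade 1 row of the later table on infusion reactions and cytokine-release syndrome says "Immediately interrupt infusion".

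**The concern.** These are stop-or-continue rules for serious immune events in patients treated after complete resection. If two rules are in force for one event and grade, re-exposure depends on which table the site happened to read, and either action is compliant.

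The trial data inherit the ambiguity. Atezolizumab exposure, discontinuation counts and deviation classification in Arm 1 all need a single rule to refer to. Section 6.1 requires major and critical deviations to be reported. Section 13.6 has treatment administration verified for every patient at selected sites. A monitor cannot classify a resumption after Grade 2 myocarditis consistently against two opposing instructions.

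German sites face an extra difficulty. Section 1.3 of the AIO appendix ends study treatment after any event that meets the Section 8.2 discontinuation criteria. A German site that resumed under the first table could be in breach if the second one governs.

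**Working it through.** The core of the point is a comparison of text. Arithmetic enters only for its size.

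**Step 1. The two myocarditis rules by grade.**

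| Grade | Myocarditis table | Myocarditis row in the pericardial table | Same atezolizumab rule? |
|---|---|---|---|
| 2 | Hold; resume if symptoms fall below Grade 2; stop for good only if they do not; consider steroids | Stop for good, no condition; start steroids | No |
| 3-4 | Stop for good; start steroids | Stop for good; start steroids | Yes |

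The conflict is confined to Grade 2. Both tables stop dosing at once; they part on whether it can return.

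**Step 2. Search for a tie-break.**

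- The short introduction on immune-mediated cardiac events covers both tables and ranks neither.
- The myocarditis section points forward to the pericardial section, which points back.
- The general text of Section 8.2.2 favours supportive care with continued dosing for Grade 1-2 immune-related events. That is a third position, not a ranking of the two tables.
- The text that refers sites to the Investigator's Brochure for certain events names neither myocarditis nor myositis.
- The AIO appendix has no atezolizumab toxicity tables of its own and refers back to Section 8.2.

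None of these says which table governs.

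**Step 3. Myositis and myelitis.** The table under the myositis heading has three rows (Grade 1, Grade 2, Grade 3 or 4), all for myelitis. Either the labels are wrong or the table is in the wrong place. In both cases one of the two events has no rows of its own. As printed, that event is myositis, which is left with the general immune-related text.

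**Step 4. Surgery.** With 14-day cycles, 42 days is 42/14 = 3 cycles. A longer hold means removal from protocol therapy under Section 8.1.7 but may be allowed under Section 8.2.2.

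**Step 5. Infusion reactions.** The later table defines its Grade 1 by fever, using consensus grading for cytokine-release syndrome. The opening text groups fever with Grade 2 reactions and there also interrupts the infusion, restarting at half rate. A Grade 1 reaction without fever does not meet the table's Grade 1 definition. So for fever both places interrupt, and for a Grade 1 reaction without fever only the opening text speaks. What differs is the grade given to the same fever, and what follows from it. For later infusions, the opening text directs oral premedication, while the table's Grade 1 row only asks the site to consider it.

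**Step 6. Size.** Section 9.4 lists myocarditis as rare but serious, below 3%, based on 3097 patients. Section 13.2 plans 350 adults per arm. 0.03 × 350 = 10.5, so at most 10 adults in Arm 1, all grades together. Myositis is in the same frequency class and has the same ceiling. The Grade 2 share is not given.

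**The case against.** The best defence is that the second myocarditis row is meant only for myocarditis together with pericardial disease. The sentence introducing that table concerns pericarditis, effusion and tamponade, and the myocarditis section refers there for associated pericarditis. This may well be the intention. But the row label carries no such limit, and pericardial disorders have their own label beside it. If combined disease is meant, the row must say so.

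On myositis, it is fair to reply that the general text of Section 8.2.2 still applies and that the announced myelitis rules do exist, under another heading. That stands. What is missing is an event-specific rule, not all guidance.

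A reader might infer that the hyperthyroidism cell flatly contradicts itself. The documents do not settle this. The neighbouring row for asymptomatic hyperthyroidism divides its cell by TSH sub-headings, and a similar sub-heading before the last bullet may have been lost when the text was extracted from the PDF. The cell needs checking against the source, all the more because asymptomatic patients with TSH below 0.1 mU/L are sent to it.

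A reader might also infer that Grade 1 infusion reactions are slowed in one place and interrupted in another. As shown above, that compares unlike grades. Only the grading needs aligning.

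**Conclusion.** Section 8.2.2 contradicts itself on atezolizumab at Grade 2 immune-mediated myocarditis, with a secondary difference on steroids. The myositis/myelitis mismatch and the two positions on surgery are also real. The hyperthyroidism cell is an item to verify, and the infusion-reaction text needs its grades aligned.

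The ceiling of 10 adults for myocarditis assumes that the Section 9.4 frequency carries over to this population and to the combination with mFOLFOX6. The documents do not test that assumption.

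Three stronger readings are not supported:

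- That sites will manage, or have managed, these events differently. The text shows only that they may.
- That all of the roughly 350 Arm 1 patients are affected. The rules bear only on those who have the event.
- That the DFS comparison is compromised. Section 13.0 analyses efficacy by randomized arm. The ambiguity can change how much drug a few patients receive, but not who is analysed or in which arm.

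Whether anyone can still receive atezolizumab is not stated. The AIO appendix plans the last treatment in Germany for February 2023, and the expedited-reporting text in Section 9.3.1 carries an effective date of August 2024.

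**What to change.** Issue one clarification memo or amendment so that each event and grade has exactly one rule:

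1. Reconcile the Grade 2 row of the myocarditis table with the Grade 2-4 myocarditis row of the pericardial table, including the steroid wording.
2. Reconcile the Immune-Mediated Myositis section with the Neurologic disorders section, so that myositis and myelitis each have rows under their own heading.
3. Reconcile Section 8.1.7 with the general text of Section 8.2.2 on interruption for surgery.
4. Check the symptomatic hyperthyroidism cell against the source document and correct it if the conflict is there.
5. Align the grading of infusion reactions between the opening of Section 8.2.2 and the later table.

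The sponsor decides which rule stands in each case; this review proposes none. If dosing has ended, the sponsor should instead record which rule governed, so that past cases and deviations are classified uniformly.

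The cost is the memo or amendment. Sample size, alpha and the planned analyses do not change.
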